7.2.7. Severity of Events and Effects

Classifications of the AE severity include the following:

Mild	Awareness of signs or symptoms, but easily tolerated and are of minor irritant type causing no loss of time from normal activities. Symptoms do not require therapy or a medical evaluation; signs and symptoms are transient.
Moderate	Events introduce a low level of inconvenience or concern to the participant and may interfere with daily activities, but are usually improved by simple therapeutic measures; moderate experiences may cause some interference with functioning.
Severe	interrupt the participant's normal daily activities and generally require systemic drug therapy or other treatment; they are usually incapacitating.

7.2.8. Anticipated Adverse Device Effects

There are no known ADEs reported with the use of the TWO2 device. The following AEs are possible secondary outcomes and must be reported in the CRFs:

Mild to Moderate Adverse Events

Mild and moderate adverse events can include, but are not necessarily limited to, the following clinical signs and symptoms:

- Pain
- Dermatitis
- Cellulitis
- New or satellite areas of breakdown
- Erythema

Severe Adverse Events

Severe adverse device effects can include, but are not necessarily limited to, the following clinical signs and symptoms:

- Infection requiring hospitalization

7.2.9. Reporting Serious Adverse Effects

Any adverse device effects (ADEs) will be recorded and if an considered serious unanticipated adverse device effect (SUADEs) will be reported to the IRB/Ethics Committee within 10 working days (CFR 21 Part 812.150(a)(1)) or sooner if required by Regulatory Authorities and institutional guidelines and in accordance with the principles of ICH GCP. Any study related occurrence that could adversely affect the safety of subjects or the conduct of the trial should be reported to AOTI Ltd. and if locally required to the local IRB/Ethics Committee by telephone and fax within 24 hours of being noted. An expedited reporting form should be used.

The information reported must at least include the following:

Name, address and telephone number of the reporting investigator.

- Title of the trial.

- Study code.
- Subject identification number, sex and year of birth.
- Description of the AE, measures taken and outcome.
- Preliminary classification of causal relationship by the investigator.

Within 48 hours of sending the initial information the investigator must send a completed copy of the form to AOTI Ltd by fax or email (where local policy allows).

AOTI Ltd Reports must be addressed to:

Study Director Contact Details for Adverse Event Reporting:

Name: [name] DProf, DMS, CRT, FCMI **Fax:** **+1** [contact] (US sites only)
Email: [contact] **Telephone:** **+1** [name]

7.2.10. *Follow-up of Adverse Device Effects*

The investigator will initiate appropriate therapeutic measures and investigations for adverse effects(s) and concurrent illness(es) that occur during the study and must treat with established standards of care. The investigator must continue to follow all serious adverse effects and those non-serious effects possibly related to a study treatment until they are resolved or until the investigator considers them to be stable. This follow-up may extend beyond the end of the trial.

7.2.11. *Reporting Safety Information*

AOTI Ltd. will promptly notify the Investigator and the Regulatory Authorities of findings that could adversely affect the safety of subjects, impact on the conduct of the trial, or alter the IRB/Ethics Committee approval/favorable opinion of the trial. The Investigator must promptly inform the relevant IRB/Ethics Committee of all occurrences deemed to involve increased risks to subjects (if required).

8. TRIAL CONDUCT

8.1.1. Overview of Screening Treatment and Follow-Up Requirements

Procedure / Examination	Screening & Start Run-In	Baseline * (2 weeks later)	1	2	3	4	5	6	7	8	9	10	11	12	12 wks Follow up	38 wks Follow up
Informed Consent	X															
In-& Exclusion criteria	X	X														
Randomization		X														
Adverse Effects and Events		X	X	X	X	X	X	X	X	X	X	X	X	X	X	X
Medical History/ Preexisting Conditions	X															
Record Concomitant Medications	X	X	X	X	X	X	X	X	X	X	X	X	X	X	X	X
Compliance assessment (treatment, dressings)		X	X	X	X	X	X	X	X	X	X	X	X	X		
Height and Weight	X															
Wound History (Duration; course of healing last 12 months and previous treatment modalities)		X														
Dressing removal / wound cleansing and re-dressing	X	X	X	X	X	X	X	X	X	X	X	X	X	X		
Wound assessment and measurement (location, size)**	X	X	X	X	X	X	X	X	X	X	X	X	X	X		
Pain assessment	X	X	X	X	X	X	X	X	X	X	X	X	X	X	X	X
Neuropathic assessment	X															
Infection Assessment	X	X	X	X	X	X	X	X	X	X	X	X	X	X		
ABI and Secondary Vascular Assessment ***	X															
Dig. Photographs (post debridement)	X	X	X	X	X	X	X	X	X	X	X	X	X	X	X	X
Debridement if needed		X	X	X	X	X	X	X	X	X	X	X	X	X		
Cardiff Wound Impact Schedule ****	X	X													X	X
Lab tests	X														X	
Punch biopsies *****		X				X										
Education on diabetic foot care/off-loading*****	X	X	X	X	X	X	X	X	X	X	X	X	X	X	X	X
Economic assessment		X				X				X				X	X	X
Device competency assessment		X				X				X						

Note: *Baseline visit window is -1/+2 days. All follow-up visit windows are +/- 2 days. 12 and 38 Week follow-up +/- 2 weeks

** Measurement recorded from central assessor report plus manual measurement at baseline

*** Secondary vascular testing only needed if not within 4 months of screening date

**** Cardiff Wound Impact Schedule (debriefing of subjects week 38 Follow up where not previously validated)

***** Optional (none for sub-study)

***** Off-loading with study boot or CROW boot where required

***** Health Economic Assessment (EQ-5D, dressing history up to 8 weeks and significant related medical events)

8.1.2. **Wound Closure Assessment**

Procedure / Examination	Wound Closure Visit # 1	Wound Closure Visit # 2
Verify Informed Consent	X	X
Adverse Events	X	X
Record Concomitant Medications	X	X
Compliance assessment (treatment, dressings)	X	X
Confirm Wound Closure Assessment	X	X
Dressing removal / wound cleansing and re-dressing	X	
Pain assessment	X	X
Dig. Photographs (post Debridement if needed)	X	X
Debridement if needed	X	X
Cardiff Wound Impact Schedule (If at week 12 on treatment or last visit before follow up)	X	X
Education on diabetic foot care/off-loading Study dressings	X	
Education on diabetic foot care/off-loading Standard of care dressings per PI/Sub I		X
Economic assessment (if week 4, 8 or 12 on treatment or last visit before follow up)	X	X

Note:

* The wound closure visits may occur within the 12 week follow up period

* Visit window is +/- 2 days.

8.2. **Assessment by Time Point**

8.2.1. **Screening Assessment**

Potential subjects should sign a written IRB/Ethics Committee approved informed consent. Inclusion criteria and exclusion criteria are checked. The index ulcer is chosen as the largest ulcer (in surface area) on the foot. The wound has to be measured and assessed. The vascular assessment is performed, and blood taken for the lab tests. Previous treatment modalities for the index ulcer attempted are documented.

If the subject meets all criteria for inclusion into the study the 2 week run-in period is initiated.

The following assessments will be done:

- 1) Obtain informed consent
- 2) Complete subject contact information and demographics
- 3) Assign subject a screening ID number
- 4) Verify subject eligibility by checking against inclusion/exclusion criteria
- 5) Quality of Life Assessment using CWIS
- 6) Medical history
- 7) Concomitant medication
- 8) Height and Weight
- 9) Tobacco use
- 10) Identify index ulcer
- 11) Wound History
- 12) Wound assessment: Location, size and appearance
- 13) Pain assessment of wound using the Visual Numerical Rating Scale
- 14) Neuropathic assessment
- 15) Infection assessment
- 16) Digital Photograph (post debridement)
- 17) Debridement if needed
- 18) Dress wound with study dressings
- 19) Vascular assessment (ABI and toe pressure or tissue pressure or TcPO2 or duplex (below knee))
- 20) Record lab data or blood sample taken to obtain values for:
 - Electrolytes
 - Creatinine

- HbA1c, blood glucose
- WBC
- Albumin and pre-albumin (where routinely available)
- CBC
- C-reactive protein

21) Provide and educate on off-loading boot/CROW boot, study dressings and diary card and ID card

22) Educate on diabetes management and foot care

23) Urine pregnancy for women of childbearing potential

The subject is supplied with the off-loading boot/CROW boot and treated with the dressings defined for this study for 2 weeks until the baseline assessment takes place.

8.2.2. *Baseline Procedures (after 2 week run-in period)*

Prospective subjects must meet all inclusion criteria to be eligible to participate in the study. Missing data for the final verification of all inclusion and exclusion criteria will be performed including HbA1c which has to be available at the baseline visit.

The following data will be collected at the baseline visit prior to randomization treatment with the TWO₂ therapy or Control therapy:

- 1) Verify Informed Consent
- 2) Record adverse events
- 3) Record changes in concomitant medication
- 4) Verify subject eligibility by checking against inclusion/exclusion criteria
- 5) Quality of Life Assessment using CWIS
- 6) Collect diary card/Compliance assessment (treatment/dressings)
- 7) Remove dressings/wound cleansing
- 8) Pain Assessment using the Visual Numerical Rating Scale
- 9) Digital photograph (post debridement)
- 10) Debridement if needed
- 11) Wound assessment: Location, size and appearance
- 12) Infection assessment
- 13) Dress wound with study dressings
- 14) Record lab data if not previously recorded
- 15) Education on diabetes management and foot care and off-loading boot/CROW boot
- 16) Dispense study dressings and diary card
- 17) Health Economic Assessment (including EQ-5D)
- 18) Punch biopsies
- 19) Device competency assessment (Completed in subjects home or equivalent after baseline clinic visit)

8.2.3. *Randomization Procedures*

Subjects will be randomized to receive either TWO₂ therapy as an adjunctive therapy or a control therapy.

8.2.4. *Weekly procedures during treatment period*

All subjects (TWO₂ therapy and control therapy) will have a weekly assessment in the clinic until the index ulcer is closed or 12 weeks have passed – whichever is sooner.

Each Assessment Visit will include the following procedures:

- 1) Verify Informed Consent
- 2) Record adverse events/device effects
- 3) Record changes in concomitant medication
- 4) Quality of Life assessment using CWIS (week 12 only)
- 5) Collect diary card/Compliance assessment (treatment/dressings)
- 6) Remove dressings/wound cleansing
- 7) Pain Assessment using the Visual Numerical Rating Scale
- 8) Digital photograph (post debridement)
- 9) Debridement if needed
- 10) Wound assessment: Location, size, depth and appearance
- 11) Infection assessment
- 12) Blood sample taken to obtain values for (**visit 12 only**):
 - Electrolytes
 - Creatinine
 - HbA1c, blood glucose
 - WBC
 - Albumin and pre-albumin (where available)
 - CBC
 - C-reactive protein
- 13) EQ-5D) (week 4, 8 and 12 only)
- 14) Education on diabetes management and foot care and off-loading boot/CROW boot
- 15) Dispense study dressings and diary card
- 16) Device competency assessment (completed in subject's home or equivalent. Week 4 and 8 only)

8.2.5 *Punch biopsies*

Punch biopsies may be taken at baseline and 4 weeks for up to 20 subjects enrolled in the study at selected centers. These subjects will have specifically agreed to this procedure on their Informed Consent Form.

The biopsies will be taken utilizing a standard 4 mm dermal punch biopsy kit and will be taken following routine debridement of the wounds to avoid collection of dead necrotic tissue. Prior to biopsy collection, the wound bed is prepared with local antiseptics. As per subject request, local anesthesia is administered. This is not standard because most subjects in this study will be insensate in the area of the wound.

In addition it is important to have some tissue samples without local anesthetic to determine whether the use of anesthetic agents impacts the molecular studies planned with the biopsy. Biopsies will be taken from the wound edge and from the center of the wound.

Samples will be collected, packed and transported per the procedure outlined by the testing laboratory instructions. The samples will be transported from clinic to the testing laboratory in properly secured biohazard-safe containers under appropriate temperature conditions.

The samples will be analyzed histologically for signs of infection, collagen and neo-angiogenesis. Additional immune-histochemical analyses for such values as VEG-F and matrix metalloproteinases (MMPs) are also envisioned.

8.2.6 *Premature Withdrawal of a Subject from the Trial*

Subjects are free to withdraw from the trial at any time without penalty or prejudice to their further treatment. Subjects may stop the trial treatment for any reason.

All subjects should be invited to do the End of Trial Visit to complete a final assessment, including wound status, complete quality of life questionnaire, etc.

The End of Trial Visit should occur on or as close as possible to treatment week 12. Though encouraged to do so in all cases, some subjects may still decline to attend this visit, in which case this will be recorded in the CRF (along with any reasons if given). Subjects who are withdrawn from the treatment will be asked if they consent to be followed up after withdrawal to determine whether their ulcer heals within the 12 weeks from randomization.

In addition, a follow-up after 12 weeks and/or 38 weeks will be undertaken wherever possible in those that were withdrawn to confirm whether they healed according to intention-to-treat (ITT).

8.2.7 *Procedures for confirmation of wound closure*

Subjects with index ulcers that are observed to close will be followed for 4 weeks to confirm wound closure. During this period, subjects will continue to receive treatment and dressing changes and wear the standard off-loading device. If wound closure occurs within the 11th week, treatment will continue for an additional 2 weeks to confirm closure (up to a maximum of 14 weeks of treatment).

The wound closure confirmation assessment will be done at confirmation visits 2 weeks after closure.

- 1) Verify Informed Consent
- 2) Record adverse events/device effects
- 3) Record changes in concomitant medication
- 4) Quality of Life Assessment using CWIS (If week 12 on treatment or last visit before follow up)
- 5) Collect diary card/Compliance assessment (treatment/dressings)
- 6) Confirm wound closure for past week
- 7) Pain Assessment using the Visual Numerical Rating Scale
- 8) Wound History: time of wound closure
- 9) Digital Photograph of the closed index ulcer
- 10) Education on diabetes management and foot care/off-loading boot/CROW boot
- 11) Dispense study dressings (confirmation visit 1 only) /dressings (if indicated confirmation visit 2) and diary card (confirmation visit 1 only)
- 12) EQ-5D (if week 4, 8 or 12 on treatment or last visit before follow up)
- 13) Blood sample taken to obtain values for (if at week 12 from randomization or at last closure visit if before):
 - Electrolytes
 - Creatinine
 - HbA1c, blood glucose
 - WBC
 - Albumin and pre-albumin (where available)
 - CBC
 - C-reactive protein

Subjects whose index ulcers are confirmed as closed will enter into the follow-up phase and will be terminated from further treatment with TWO2 therapy or Control therapy. Subjects will be encouraged to continue to wear the standard off-loading boot/CROW boot during the follow-up phase.

8.2.8 12 Week Follow up

All subjects will be reviewed and followed up 12 weeks after “wound closure” or the 12-week “end of treatment phase”, whichever is sooner +/- 2 weeks. Data for 12 week follow up analysis will be collected per the subject’s preference by telephone or in the clinic if attending a routine visit for wound care. Index ulcers not yet healed, will continue to be treated with best available therapy as determined by the treating medical provider.

The following assessments will be performed on all subjects:

- 1) Verify Informed Consent
- 2) Record adverse events
- 3) Record changes in concomitant medication
- 4) Quality of Life Assessment using CWIS
- 5) Pain Assessment using the Visual Numerical Rating Scale (where possible, if applicable)
- 6) Digital Photograph of the open index ulcer
- 7) Health Economic Assessment (including EQ-5D)
- 8) Education on diabetes management (and foot care/off-loading when indicated)

8.2.9 38 Week Follow up

The 38 week follow up will take place 26 weeks +/- 2 weeks from the time of the last study visit (12 week follow up). Data for 38 week follow up analysis will be collected per the subject’s preference by telephone or in the clinic if attending a routine visit for wound care. Index ulcers not yet healed, will continue with best available therapy as determined by the treating medical provider.

- 1) Verify Informed Consent
- 2) Record adverse events
- 3) Record changes in concomitant medication
- 4) Quality of Life Assessment using CWIS
- 5) Pain Assessment using the Visual Numerical Rating Scale (where possible, if applicable)
- 6) Digital Photograph of the open index ulcer (where possible)
- 7) Health Economic Assessment (including EQ-5D)
- 8) Education on diabetes management (and foot care/off-loading when indicated)
- 9) Debriefing of subjects where CWIS not previously validated

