
[figure not shown]
All subjects whose wounds are confirmed closed or who finished the treatment phase of 12 weeks – whichever is sooner - will enter into the post-treatment follow-up phase of 12 and 38 weeks.

Subjects who are withdrawn by the PI/Subl from the study treatment phase will be asked to return for the final week 12 on treatment visit and follow-up phase at 12 and 38 weeks.

The maximum duration for participation in the trial is 54 weeks. During the follow-up phase, subjects will receive standard care according to the clinician's recommendation and will be asked not to participate in another wound care trial in this period.

The start of the trial is scheduled for July 2014.

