3.2. Flowchart of Subject Flow

3.3. Endpoints

3.3.1. Primary Study Endpoints

The primary endpoint is the:

Incidence of complete wound closure within 12 weeks.

Closure is defined as 100% skin re-epithelialization without dressing requirements which is confirmed by 2 consecutive study visits 2 weeks apart.

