7. ASSESSED VARIABLES

7.1. Efficacy Assessment

7.1.1. Primary Efficacy Assessment

The primary endpoint is the “Incidence of complete wound closure within 12 weeks”.

Only one ulcer (the index ulcer) will be assessed per subject. In subjects with multiple ulcers, this will be the largest ulcer present fulfilling all other inclusion criteria.

Closure is defined as skin re-epithelialization without drainage or dressing requirements which is confirmed at 2 consecutive trial visits 2 weeks apart.²³

Wound closure checks will be performed weekly. The closure of the wound is a clinical judgment by the investigator. A digital picture reviewed by the central assessor will also provide evidence of wound closure.

Ulcers will be measured by the central assessor. A deidentified digital photograph of the ulcer will be taken with and transmitted by the study sites using a wifi/wireless enabled tablet device. The ulcer's surface area, circumference, maximum and minimum diameters will be recorded at baseline assessment of the subject.

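### For withdrawn subjects, 8.2.6 confirms ITT healing by a late and possibly telephone contact that cannot meet the closure definition, and 9.5 contradicts 9.2 on scoring missing primary outcomes

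*Combined protocol and SAP*

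**What the plan says.** **Endpoint.** Section 3.3.1 reads: "Closure is defined as 100% skin re-epithelialization without dressing requirements which is confirmed by 2 consecutive study visits 2 weeks apart". Section 7.1.1 repeats that closure is "confirmed at 2 consecutive trial visits 2 weeks apart", and makes it the investigator's clinical judgment, supported by a photograph sent to the central assessor.

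**Withdrawn subjects.** Section 8.2.6 invites everyone to an End of Trial Visit near week 12, and seeks "consent to be followed up after withdrawal to determine whether their ulcer heals within the 12 weeks from randomization". It then adds that a follow-up after 12 and/or 38 weeks "will be undertaken wherever possible in those that were withdrawn to confirm whether they healed according to intention-to-treat (ITT". Section 3.1 says that subjects withdrawn by the investigator "will be asked to return for the final week 12 on treatment visit and follow-up phase at 12 and 38 weeks". Section 4.3 lists the same three contacts.

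**General visit text.** Under 8.2.4 all subjects "will have a weekly assessment in the clinic until the index ulcer is closed or 12 weeks have passed". Section 8.2.7 opens with any index ulcer seen to close and sets a confirmation visit 2 weeks after closure, but adds: "During this period, subjects will continue to receive treatment and dressing changes and wear the standard off-loading device". The note to 8.1.2 allows closure visits to fall in the follow-up period.

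**Scoring.** Section 9.2 makes ITT the primary population, follows all participants to week 12, and counts death, amputation and loss to follow-up as treatment failures. Section 9.5 plans no imputation, omits subjects with missing data from the relevant analysis, and gives death and refusal as examples of why a main outcome may be missing. Section 9.1 makes no allowance for loss because every patient is expected to be healed or unhealed at 12 weeks.

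**The concern.** The contact that 8.2.6 assigns to confirm ITT healing is not one at which the defined endpoint can be observed. If followed literally, it could record as healed an ulcer that closed after week 12 on other therapy. It could also record as not healed an ulcer that closed in time and later reopened. The Synopsis times the interim analyses by completion of 12 weeks, so a status settled at 38 weeks could also change after an interim test.

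The second problem is scoring. The same subject can be a failure under 9.2 and absent under 9.5. For some withdrawn subjects neither section gives a clear answer. These choices affect the primary ITT result and, as written, could be made after the data are seen.

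**Working it through.** **1. Timing of the late contacts.** The 12-week follow-up is 12 ± 2 weeks after closure or the end of the treatment phase (8.2.8), so 10–14 weeks. The 38-week follow-up is a further 26 ± 2 weeks (8.2.9), so 10 + 24 = 34 to 14 + 28 = 42 weeks. The definition needs 2 weeks.

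**2. Content of the late contacts.** Both may be by telephone at the subject's preference. The lists in 8.2.8 and 8.2.9 include a photograph of an open ulcer only. Table 8.1.1 marks photographs at both follow-ups but no wound assessment. Unhealed ulcers meanwhile receive whatever therapy the treating provider thinks best. The contact therefore cannot supply the second of two visits 2 weeks apart, and cannot by itself date closure to within 12 weeks.

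The contact in 8.2.6 is not simply week 12 from randomization. It is introduced as an addition to the week-12 End of Trial Visit, and 3.1 and 4.3 list it separately from week 12.

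**3. Is there a valid route to confirmation?**

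| Text | Covers withdrawn subjects? |
|---|---|
| 8.2.4 weekly checks | Worded for all subjects |
| 8.2.7 confirmation visit | Opening is general; next sentence presumes continued treatment |
| 8.1.2 note | Allows closure visits in follow-up; does not assign them to withdrawn subjects |
| 3.1, 4.3, 8.2.6 | Name withdrawn subjects; list no 2-week closure visit |

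A valid route can be inferred but is not stated for these subjects.

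**4. Scoring rules.**

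| Subject | 9.2 | 9.5 |
|---|---|---|
| Dies or is lost before week 12 | Failure | Omitted, if the outcome is treated as missing |
| Withdrawn, declines the week-12 visit | No explicit rule | Omitted, if the outcome is treated as missing |
| Withdrawn, one unconfirmed closure | No explicit rule | Unclear whether this is missing |

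The first row is a contradiction; the other two are gaps.

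**5. The plan's sample size.** Inputs from 9.1: 43% v 64%, 80% power, no continuity correction. With p̄ = 0.535,

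n per arm = [z(1−α/2)·√(2p̄(1−p̄)) + z(0.80)·√(p₁(1−p₁) + p₂(1−p₂))]² / (p₂−p₁)².

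- α = 0.05: (1.960 × 0.7054 + 0.8416 × 0.6896)² / 0.0441 = 87.4, so 88.
- α = 0.022: (2.290 × 0.7054 + 0.8416 × 0.6896)² / 0.0441 = 109.3, so 110.

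Both stated figures reproduce. Single-look power with 110 per arm at 0.022 is 80.3%.

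**6. Illustration of the scoring choice.** The withdrawn share w is an assumption (5–20%, equal in both arms). Every withdrawn subject is taken as affected, and their ulcers close at the planned rates.

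- Not healed: rates are multiplied by (1 − w), so the difference is 21.0 × (1 − w).
- Omitted: the difference stays at 21.0 points on 110 × (1 − w) per arm.
- Late report counted, with a fraction f of ulcers open at week 12 closed by then: control 0.43 + 0.57wf, active 0.64 + 0.36wf, so the difference is 21.0 × (1 − wf).

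| w | Not healed: rates, difference, single-look power | Omitted: n per arm, single-look power | Late report: difference for f = 0 to 1 |
|---|---|---|---|
| 5% | 40.9% v 60.8%, 19.95 points, 75.3% | 104.5, 77.9% | 21.0 to 19.95 points |
| 10% | 38.7% v 57.6%, 18.9 points, 70.0% | 99, 75.4% | 21.0 to 18.9 points |
| 20% | 34.4% v 51.2%, 16.8 points, 59.1% | 88, 69.6% | 21.0 to 16.8 points |

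Single-look power understates the three-look design. Simulating looks at 37, 73 and 110 per arm, each at 0.022, gives 84.6% at the planned rates. With not-healed scoring it gives 80.5%, 76.0% and 65.5% at w = 5%, 10% and 20%.

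**The case against.** The strongest reply is that 8.2.6 replaces nothing. Its sentence adds to a week-12 visit and to consented follow-up to week 12, and no text waives the definition or the 12-week limit. An ulcer that closes after week 12 is not healed under the endpoint as written. Sections 8.2.4 and 8.2.7, with the 8.1.2 note, can be read to give a withdrawn subject a valid pair of visits. For subjects who die or are lost, 9.2 is specific to the 12-week endpoint, 9.1 cross-refers to it, and 9.5 is general.

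Much of this stands, and it rules out several stronger readings.

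- A reader might infer that withdrawn subjects have no route to a closure visit. The opening of 8.2.7 is too general for that.
- A reader might infer that 8.2.6 redefines the endpoint. It is loose wording that permits a late report to be used, not a rule that requires it.
- A reader might take the power figures as harm caused by 8.2.6. They come from scoring withdrawn subjects as not healed, which is the rule recommended below. They also assume that withdrawn active subjects still heal at 64% off the device. If those subjects heal at 43%, the true ITT difference at 10% withdrawal is 0.64 × 0.9 + 0.43 × 0.1 − 0.43 = 18.9 points, the same as under not-healed scoring.
- A reader might infer a false-positive risk from late reports. In the illustration they only shrink the difference.
- A reader might infer from 4.3, which offers continued visits to those removed for reasons other than non-compliance, that non-compliant subjects go unobserved. Sections 3.1, 8.2.6 and 9.2 contain no such exclusion, so this is a wording mismatch.

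The reply does not remove the stated purpose in 8.2.6, which ties the late contact to ITT healing. Nor does it reconcile 9.5, which itself names death as a reason for a missing main outcome, with 9.2, which calls death a failure.

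**Conclusion.** The point holds and is minor. Section 8.2.6 gives the late contacts a role in ITT healing that they cannot fill under the closure definition. The 2-week closure visit can be inferred for withdrawn subjects but is not assigned to them. Sections 9.2 and 9.5 contradict each other for death and loss to follow-up, and 9.2 has no explicit rule for a declined week-12 visit or a single unconfirmed closure.

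The size cannot be fixed from the documents, which give no withdrawal rate. Under the assumptions above, the scoring choice moves the planned difference by at most 1.05, 2.1 or 4.2 points at 5%, 10% or 20% withdrawal. These are upper bounds for equal withdrawal in both arms, and they do not show that the trial's conclusion would change. The case for acting is that the primary outcome should have one scoring rule, fixed in advance.

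**What to change.** 1. In 8.2.6, state that the 12- and 38-week contacts do not determine the primary endpoint and serve only secondary or sensitivity analyses.
2. In 9.2 and 9.5, state that every randomized subject without confirmed closure counts as not healed in the primary ITT analysis, and that omission under 9.5 does not apply to the primary endpoint.
3. In 8.2.6 and 8.2.7, state that a withdrawn, consenting subject found closed by week 12 attends the existing wound closure visit #2 in person 2 weeks later, off device.

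**Cost.** A few sentences and one already-defined visit for a few people. At the planned healing rates the number of visits is at most 220 × w × (0.43 + 0.64)/2, or about 6, 12 or 24 at 5%, 10% or 20% withdrawal.

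**Downside.** Subjects who decline count as not healed, so some power is lost. If withdrawal differs by arm, not-healed scoring can itself create a difference. With equal true healing of 43%, 10% withdrawn on active and 20% on control, and none of them confirmed, it gives 0.43 × 0.90 − 0.43 × 0.80 = 4.3 points. That is a reason to report withdrawal by arm and to keep the late reports for a sensitivity analysis.

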6. TRIAL TREATMENT MODALITIES

6.1. Trial Treatment

The TWO₂ group will receive topical oxygen as an adjunctive treatment to standard of care treatment. The TWO₂ treatment consists of the Topical Wound Oxygen therapy system (AOTI Ltd.) as well as an oxygen concentrator. Oxygen will be delivered to the device at a flow rate of at least 10 liters/ minute.

After connecting the TWO₂ Single patient-use leg chamber to the controller and concentrator, the controller initiates 4 phases of the treatment:

Phase 1:

The outer leg chamber is inflated. The limb with the ulcer can then be placed into the chamber.

Phase 2:

The integrated cuff is inflated to seal the inside of the chamber against the limb.

Phase 3:

The therapy phase: Cyclical pressurized oxygen is delivered to the limb inside the chamber.

Phase 4:

The cuff and outer leg chamber is deflated and removed from subject's limb.

This setup delivers cyclical pressurized oxygen to the wound site within a sealed and humidified environment.

The affected limb will be placed in the chamber for 90 minutes daily, 5 days a week, for a period of up to 12 weeks (plus an additional 2 visits, 2 weeks apart to confirm wound closure for index ulcers closing at week 9 or later) or until full closure of the wound, whichever is sooner.

All treatments can be done with or without removing the dressings.

The picture below shows the TWO₂ Single patient-use leg chamber and the controller.

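### The protocol gives two conflicting rules for confirming wound closure: 2 weeks with one further visit (3.1), or 4 weeks with two further visits (opening of 8.2.7, and 6.1)

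*Combined protocol and SAP*

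**What the plan says.** **The 2-week rule.** Section 3.1 treats the first closed visit as confirmatory visit 1 of 2, continues treatment for 2 more weeks, and carries the treatment phase past week 12 only for closures from week 11 onward. Sections 3.3.1 and 7.1.1 define closure by two consecutive visits 2 weeks apart. Section 8.1.2 schedules two closure visits. Later text in 8.2.7 fits this rule: for closure in the 11th week, "treatment will continue for an additional 2 weeks to confirm closure (up to a maximum of 14 weeks of treatment"; on timing, "The wound closure confirmation assessment will be done at confirmation visits 2 weeks after closure"; and the procedure list distinguishes a visit 1 and a visit 2, as in "Dispense study dressings (confirmation visit 1 only".

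**The 4-week rule.** Section 8.2.7 opens with "Subjects with index ulcers that are observed to close will be followed for 4 weeks to confirm wound closure", and then says "During this period, subjects will continue to receive treatment and dressing changes and wear the standard off-loading device". Section 6.1 sets treatment at up to 12 weeks, "plus an additional 2 visits, 2 weeks apart to confirm wound closure for index ulcers closing at week 9 or later".

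**What hangs on confirmation.** Under 8.2.7, subjects with confirmed closure "will be terminated from further treatment with TWO2 therapy or Control therapy". The dose is set in 6.1: "The affected limb will be placed in the chamber for 90 minutes daily, 5 days a week".

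**The concern.** Section 8.2.7 is the procedure that sites follow to confirm the primary endpoint, and 6.1 is where they look up treatment duration. Both contain text that disagrees with 3.1 on how long a closed ulcer is watched and treated, and on how many visits follow the first closed one.

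Two things are at stake. The first is exposure: device therapy ends at confirmation, so the length of the confirmation period sets the number of sessions given after closure. The second is how an early reopening is recorded. Section 7.1.2 defines recurrence as a break in the epithelium after complete healing. An ulcer closed at +2 weeks and open at +4 weeks is healed with a recurrence under the 2-week rule. A site working to 4 weeks could record it as never confirmed, which would remove one primary success and one recurrence event.

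**Working it through.** **Inputs.** Treatment phase 12 weeks (3.1); maximum 14 weeks of treatment (8.2.7); confirmation period 2 weeks (3.1) or 4 weeks (opening of 8.2.7); extension threshold week 11 (3.1) or week 9 (6.1); 5 sessions per week (6.1).

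**1. Reproduce the stated maximum.** Latest closure week + confirmation period = 12 + 2 = 14 weeks. This is the figure in 8.2.7.

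**2. Confirmation week by closure week.**

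| First closed | +2 weeks | Past week 12? | +4 weeks | Past week 12? |
|---|---|---|---|---|
| Week 8 | 10 | no | 12 | no |
| Week 9 | 11 | no | 13 | yes |
| Week 10 | 12 | no | 14 | yes |
| Week 11 | 13 | yes | 15 | yes |
| Week 12 | 14 | yes | 16 | yes |

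**3. Which period does each threshold imply?** If extension starts at closure week *t*, the period *p* must satisfy (*t* − 1) + *p* ≤ 12 and *t* + *p* > 12.

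- Section 3.1, *t* = 11: 10 + *p* ≤ 12 and 11 + *p* > 12, so *p* = 2 whole weeks.
- Section 6.1, *t* = 9: 8 + *p* ≤ 12 and 9 + *p* > 12, so *p* = 4 whole weeks.

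The week-9 threshold in 6.1 and the opening of 8.2.7 therefore point to the same 4-week rule. Under the 2-week rule, closures at weeks 9 and 10 are confirmed by weeks 11 and 12 and need no extension.

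**4. Sessions after first closure.** 2 weeks × 5 = 10; 4 weeks × 5 = 20. The difference is up to 10 sessions per subject whose ulcer closes.

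**5. Participation time.** Run-in 2 + treatment 12 + confirmation 2 + follow-up 38 = 54 weeks, the maximum stated in 3.1. A 4-week period would give 2 + 12 + 4 + 38 = 56. This is weak support for the 2-week rule, because 2 + 12 + 12 + 26 = 52 plus a 2-week visit window is also 54.

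**6. Sample size.** The inputs in 9.1 (43% against 64%, 80% power, significance level 0.022) reproduce 110 per arm. The confirmation period is not an input.

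**The case against.** **The 14-week maximum need not be broken.** A reader might infer from the table that the opening of 8.2.7 contradicts the maximum in its own paragraph, since closures at weeks 11 and 12 would need 15 and 16 weeks. The text does not force this. The late-closure sentence can be read as a specific exception to the general one: earlier closures get 4 weeks (10 + 4 = 14) and late ones get 2 (11 + 2 = 13, 12 + 2 = 14). On that reading nothing exceeds 14. The objection stands, and the conflict that remains is with 3.1.

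**The endpoint can still be derived.** Ulcers are photographed at treatment visits (3.1) and at both closure visits (8.1.2), and a central assessor reviews the images (7.1.1). Where closure visits fall at +2 and +4 weeks, the dated records at first closure and at +2 still allow the 2-week definition to be applied. This also stands. Reclassification is possible rather than established, and it would require a site to follow the 4-week text and the analysis to accept its record.

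**The 2-week rule is not beyond dispute.** Sections 3.3.1 and 7.1.1 fix the interval but do not say whether the first closed visit is one of the two. First closure followed by visits at +2 and +4 also fits their wording; only 3.1 settles the count. This stands in part: 3.1, the two visits in 8.1.2, the timing line in 8.2.7 and the 12 + 2 arithmetic all favor 2 weeks, but no clause says which section prevails.

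**The extra treatment may be limited in practice.** Section 8.2.7 ends therapy at confirmation and times confirmation 2 weeks after closure. A site that gives those lines priority would stop at 10 sessions. That describes one way of resolving the conflict and does not remove it.

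**Conclusion.** The conflict is real and lies in operative text. Section 3.1 gives a 2-week rule with one further visit and extension from week 11; the opening of 8.2.7 and the parenthesis in 6.1 give a 4-week rule with two further visits and extension from week 9. Sites could give 10 or 20 post-closure sessions, confirm the primary endpoint at different times, and differ on how to record an ulcer that reopens between +2 and +4 weeks.

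The number of subjects reclassified is unknown, because the documents give no reopening rate for that interval. A reader might take the expected number of closures under the planned rates as the size of the problem, but that counts the subjects to whom the instructions apply, not errors. A reader might also infer bias between arms or lost power. Neither is shown: both arms are blinded and receive the same instructions, and the total of 220 is unaffected.

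The conclusion assumes that 3.1 states the intended rule. It should be corrected because the fault sits in the instructions for confirming the primary endpoint and the correction is nearly free.

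**What to change.** **Section 8.2.7.** In the opening sentence, change the follow-up from 4 weeks to 2. Extend the late-closure sentence from the 11th week alone to week 11 or later, as in 3.1, so that week-12 closures are covered explicitly. Replace the plural confirmation visits with a single confirmation visit 2 weeks after the first closed visit.

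**Section 6.1.** Replace the parenthesis with this rule: the first closed visit is confirmatory visit 1; one further visit follows 2 weeks later; treatment goes beyond week 12 only for closures at week 11 or later, to a maximum of 14 weeks.

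**Before amending,** the sponsor should confirm that the 3.1 rule is the intended one.

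**Cost.** A few words in two sections and a matching instruction in the CRF and site training. There are no new visits, since 8.1.2 already schedules two closure visits, and no change in sample size.
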